## 3. STUDY DESIGN

## **3.1. GENERAL DESCRIPTION**

This is a Phase 3, randomized, double-blind, placebo-controlled, in-patient, safety, and efficacy study to evaluate HP-3070 for the treatment of schizophrenia.

This study will consist of a Screening/placebo Run-in Period of 3 to 14 days, a 6-week double-blind Treatment Period and a 30 day Follow-up Period.

Subjects will be hospitalized at the Screening Visit and will remain hospitalized during the study. The subject may leave the hospital study for necessary personal business. Any subject who leaves the site must have an alcohol breathalyzer and urine drug tests when they return to the site.

After obtaining informed consent, each subject will be assigned a unique subject number. Eligible subjects will be hospitalized for the duration of the study. While undergoing screening procedures and waiting for results of laboratory tests, ECGs, and other assessments, the subject will start treatment with the single-blind placebo patch. The subject must have the single-blind placebo patch applied for a minimum of 3 days prior to being randomized into the double-blind Treatment Period. In addition, current antipsychotic and other prohibited medications will be washed out during the run-in period and must be completed prior to randomization into the double-blind treatment period. Details in regard to wash-out periods for specific drugs are summarized in Protocol Section 5.10.1. Subjects who have a decrease in PANSS total score ≥20% from Screening to Baseline or a PANSS total score <80 at Screening or Baseline will be discontinued from the study and will not enter the double-blind Treatment Period.

Document:	\\quintiles.net\Enterprise\Apps\sasdata\SASb\SAS\Noven\HP-			
Documenti	3070\XWA17541\Biostatistics\Docu	imentation\SAP\Final 6\Noven HP-3070-GL-04 S/	AP text Final	
	6_18Jan2018.docx			
Author:	[name]	Version Number:	Final 6	
		Version Date:	18Jan2018	
Template No:	CS TP BS016 – Revision 3	Reference: C	CS WI BS005	

Effective Date: 01May2012

Copyright © 2012 Quintiles Transnational Corp. All rights reserved.

Noven Pharmaceuticals, Inc. STATISTICAL ANALYSIS PLAN: PROTOCOL HP-3070-GL-04 Page 12 of 50

Subjects eligible for randomization into the double-blind Treatment Period will be randomly assigned to HP-3070 9.0 mg, HP-3070 18.0 mg, or placebo in a 1:1:1 ratio stratified by country. Subjects will receive treatment with study medication daily for 6 weeks.

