The study will evaluate 9.0mg (HP-3070 9.0 mg) and 18.0 mg (HP-3070 18.0 mg) of HP-3070 transdermal patches versus placebo transdermal patches. Patches will be applied by site personnel at approximately the same time daily and each patch will be worn for 24 hours. Every day, 24 hours (±15 minutes) after patch application, site personnel will remove previous day's patches and apply new patches.

All subjects will have a follow-up contact (site visit or telephone call, at the discretion of the Investigator) 30 days after the last patch is removed. This contact will be used to collect information about any Adverse Events (AEs) or Serious Adverse Events (SAEs) that may have occurred since discharge and to follow-up on any Adverse Events (AEs) that were on-going at discharge.

Assuming an effect size of 0.35 on the change in PANSS total score from baseline to Week 6 for the two pairwise comparisons between each active HP-3070 treatment arm and placebo, the power for detecting a statistically significant HP-3070 advantage will be approximately 0.90 having 204 evaluable subjects per each treatment arm, using a two-sided alpha level of 0.025 for each comparison. A two-sided overall type I error is equal to 0.05. Having three treatment arms, the total number of subjects randomized in the trial and included in primary analysis set will be approximately 612.

The effect size of 0.35 (difference between means equal to 7 and common standard deviation (SD) equal to 20) was chosen based on the lowest effect size observed in results from the studies conducted with sublingual (SL) asenapine and approved by the Food and Drug Administration (FDA) (Sycrest®/SAPHRIS® [Study 041004, and Study 041023]).

A sample size recalculation (SSR) will be conducted as described in Section 4.2 on the blinded data after approximately 50% of the originally planned number of subjects have been randomized and completed up to 6 weeks of study treatment.

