# **13.** STUDY MEDICATION COMPLIANCE

Compliance with study medication during the double-blind period will be summarized for the ITT analysis set.

During the double-blind Treatment Period (Day 1 through Day 42) site personnel will apply 2 patches once daily to subjects as randomized. Patches will be applied by site personnel at approximately the same time every day and each patch will be worn for 24 hours.

If both patches are detached completely then 2 new patches from the subject's kit should be applied immediately, provided that there is at least 6 hours of time remaining before the next dose. If only one patch detaches completely, then the other patch should also be removed and 2 new patches from the subject's kit should be applied immediately, provided that there is at least 6 hours of time remaining before the next dose.

Document:	\\quintiles.net\Enterprise\Apps\sasdata\SASb\SAS\Noven\HP- 3070\X\\\A17541\Biostatistics\Documentation\SAP\Einal 6\Noven HP-3070-GL-04 SAP text Einal			
	6_18Jan2018.docx			
Author:	[name]	Version Number:	Final 6	
		Version Date:	18Jan2018	
Template No: CS_TP_BS016 – Revision 3 Effective Date: 01May2012		Reference:	CS_WI_BS005	

Copyright © 2012 Quintiles Transnational Corp. All rights reserved.

Noven Pharmaceuticals, Inc. STATISTICAL ANALYSIS PLAN: PROTOCOL HP-3070-GL-04 Page 24 of 50

Number and percentage of subjects who are compliant (defined as using  $\geq$  80% and  $\leq$  120% of study medication) and noncompliant (defined as using less than 80% or more than 120% of study medication) during any evaluation period will be presented.

Compliance will be summarized for periods between every double-blind treatment period visit (Weeks 1 through 6) and double-blind period overall.

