#### 15.1.3. PRIMARY ANALYSIS OF PRIMARY EFFICACY VARIABLE

The primary efficacy analysis will be performed for the Full Analysis Set.

The estimand in the primary analysis for efficacy for each dose is the difference between treatments groups (HP-3070 dose group vs. placebo) in the change from Baseline to Week 6 in PANSS total score in all subjects as randomized, under the assumption that all randomized patients remain on their randomized treatment throughout the trial. PANSS scores obtained 24 hours after removal of the double-blind study medication on Day 42 or PANSS scores obtained more than 24 hours after discontinuation of double-blind study medication and the subject switched to an approved antipsychotic treatment will be excluded as outliers. Outliers will be defined *a priori* as (i) PANSS total scores obtained more than 24 hours after removal of double-blind study medication on Day 42; or (ii) PANSS total scores obtained more than 24 hours after discontinuation of double-blind study medication and the subject switched to an approved antipsychotic treatment. Non-compliance/non-adherence to study treatment may lead to poor outcomes and introduce variability. The terminal half-life of asenapine from Saphris/Sycrest is 24 hours and the mean half-life of asenapine from HP-3070 patch ranged from 29.7 hours to 31.3 hours for all the application sites.

Considerable efforts will be made during the study conduct to prevent outliers. For example: site personnel will be instructed to not issue a day pass to patients on Day 41 (last day of double-blind patch application) and patients will be allowed to leave the clinic only after all Day 42 (Week 6) assessments are complete. Subjects without PANSS total score at Week 6 will be modeled as similar to those with data conditional on observed response history and covariates. All discontinued subjects will be assessed with PANSS total score at the time of treatment discontinuation.

The primary efficacy variable, change from Baseline to Week 6 in the PANSS total score for each of the 3 treatment arms, will be analyzed using an MMRM analysis. The MMRM model will include change from Baseline

Document:	\\quintiles.net\Enterprise\Apps\sasdata\SASb\SAS\Noven\HP- 3070\XWA17541\Biostatistics\Documentation\SAP\Final 6\Noven HP-3070-GL-04 SAP text Final		
Author:	6_18Jan2018.docx [name]	Version Number:	Final 6
		Version Date:	18Jan2018
Template No: CS_TP_BS016 – Revision 3		Reference:	CS_WI_BS005

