# **16.1. TREATMENT EMERGENT ADVERSE EVENTS**

Adverse events will be coded using MedDRA central coding dictionary, version 20.1 . Severity for AEs is classified in the eCRF as 'mild', 'moderate', or 'severe'.

Treatment Emergent Adverse Events (TEAEs) are defined as AEs that first occurred or worsened in severity after the first administration of the study drug.

TEAEs during the double-blind treatment period is defined as an AE with a start date on or after the date of first dose of double-blind study medication through the 30 day follow-up period. The same rule applies for Run-in Period (for those enrolled in the double-blind period)

SAEs that occur within 30 days after last dose of double-blind study medication will be reported.

In the case where it is not possible to define an AE as treatment-emergent or not, the AE will be classified by the worst case i.e. treatment-emergent.

Adverse event summaries will include numbers of events and subject incidence (number and percentage of subjects with at least one event) by treatment group and further categorization as described below.

An overview of AEs within each of the categories described below will be provided:

- AEs (for those who enrolled in the double-blind period) which occurred during the single-blind run-in or double-blind period
- TEAEs
- TEAEs by highest severity
- TEAEs by strongest relationship to study medication (Not Related, Related)
- TEAEs leading to study medication discontinuation
- Serious TEAEs
- Serious TEAEs by strongest relationship to study medication (Not Related, Related)
- TEAEs leading to death
- Commonly occurring TEAEs (defined as those which occur in 5% or more of the subjects in any treatment arm)
- TEAEs at the patch application site

Document:	\\quintiles.net\Enterprise\Apps\sasdata\SASb\SAS\Noven\HP-		
	3070\XWA17541\Biostatistics\Documentation\SAP\Final 6\Noven HP-3070-GL-04 SAP text Final		
	6_18Jan2018.docx		
Author:	[name]	Version Number:	Final 6
		Version Date:	18Jan2018
Template No:	CS_TP_BS016 - Revision 3	Reference: (	S WL BS005

Effective Date: 01May2012

Copyright © 2012 Quintiles Transnational Corp. All rights reserved.

Noven Pharmaceuticals, Inc. STATISTICAL ANALYSIS PLAN: PROTOCOL HP-3070-GL-04 Page 34 of 50

Multiple occurrences of the same category of AEs will be counted once for each subject, at the highest severity and strongest relationship to study medication as appropriate.

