#### **16.1.6. AEs at Patch Application Site**

Spontaneous complaints of dermal reactions (skin irritation, discomfort) will be recorded as AEs. Spontaneous reports might include but are not limited to the following: initial dermal response and exacerbation of an existing response. AEs at the patch application site will be summarized by PT and severity for the events occurring during the double-blind period. A subject data listing of AEs at the patch application site will be provided.

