#### Table 14.3.1.2 Treatment-Emergent Adverse Events During the Double-Blind Period by System Organ Class and Preferred Term Safety Analysis Set

	HP-3070 18.0 mg	HP-3070 9.0 mg	Placebo
System Organ Class	(N=xxx)	(N=XXX)	(N=XXX)
Preferred Term	n (%)	n (%)	n (%)
Total number of TEAE	XX	XX	XX
Subjects with any TEAE	xx (xx.x)	xx (xx.x)	xx (xx.x)
SYSTEM ORGAN CLASS 1	xx (xx.x)	xx (xx.x)	xx (xx.x)
Preferred Term 1	xx (xx.x)	xx (xx.x)	xx (xx.x)
Preferred Term 2	xx (xx.x)	xx (xx.x)	xx (xx.x)
	xx (xx.x)	xx (xx.x)	xx (xx.x)
SYSTEM ORGAN CLASS 2	xx (xx.x)	xx (xx.x)	xx (xx.x)
Preferred Term 1	xx (xx.x)	xx (xx.x)	xx (xx.x)
Preferred Term 2	xx (xx.x)	xx (xx.x)	xx (xx.x)
	xx (xx.x)	xx (xx.x)	xx (xx.x)

Note: TEAE = Treatment-Emergent Adverse Event, AE = Adverse Event, N = number of subjects in the safety analysis set by treatment group.

Note: TEAEs are defined as all AEs which start (or increase in severity) prior to, on or after the date of first dose of doubleblind study medication through the 30 day follow-up period.

Note: Percentages are calculated as (n/N) \* 100.

Note: Subjects with multiple events in the same category are counted only once in that category. Subjects with events in more than one category are counted once in each of those categories.

Note: This summary is sorted by decreasing frequency of system organ class, and within system organ class, by decreasing frequency of preferred term in the HP-3070 18.0mg column.

Note: Adverse events are coded using Medical Dictionary for Regulatory Activities (MedDRA) Version xx.x.

Noven\HP-3070\XWA17541\Biostatistics\Production\Tables\xxxxx.sas ddmmmyyyy hh:mm Programming note: SOC should be displayed in all caps. Preferred Term should include lower case.

Author: [name]

Version Number: Version Date: Draft 2 09Jan2017 Page **76** of **144** 

IMS Health & Quintiles are now

Noven Pharmaceuticals, Inc. Protocol HP-3070-GL-04 Page 1 of x

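### Adverse-event tables titled for the double-blind period also count the 30-day off-drug follow-up, so no planned table gives on-treatment incidence

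*SAP*

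**What the plan says.** **Window.** Section 16.1 sets this double-blind window: "an AE with a start date on or after the date of first dose of double-blind study medication through the 30 day follow-up period". Footnotes to Tables 14.3.1.1, 14.3.1.2, 14.3.1.3, 14.3.1.5 and 14.3.1.14 give the same end point. Tables 14.3.1.4 and 14.3.1.6 to 14.3.1.13 are modelled on these and inherit it.

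**Titles.** From Table 14.3.1.2 on, the titles name the double-blind period, for example "Treatment-Emergent Adverse Events During the Double-Blind Period by System Organ Class and Preferred Term".

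**Periods.** Section 3.1 describes "a 6-week double-blind Treatment Period and a 30 day Follow-up Period" as two separate periods. Section 13 dates the first: "During the double-blind Treatment Period (Day 1 through Day 42". Section 16.1 arranges the adverse-event listings by study period according to onset date, and Listing 16.2.3.1.1 codes single-blind, double-blind and follow-up separately.

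**Collection after treatment.** Section 3.1 places one visit or telephone call "30 days after the last patch is removed" and states its purpose: "This contact will be used to collect information about any Adverse Events (AEs) or Serious Adverse Events (SAEs) that may have occurred since discharge".

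**Patch-site events.** Section 16.1.6 says that "AEs at the patch application site will be summarized by PT and severity for the events occurring during the double-blind period". The footnote of Table 14.3.1.14, which reports them, runs through follow-up.

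**Drug after removal.** Section 15.1.3 states that "the mean half-life of asenapine from HP-3070 patch ranged from 29.7 hours to 31.3 hours". When it defines PANSS outliers, the same section foresees a switch to an approved antipsychotic after stopping.

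**The concern.** A reader of a table titled for the double-blind period will take its percentages as incidence while on randomised treatment. They are not. They combine six weeks of inpatient observation, with daily patch changes by site staff, and thirty days off drug that are covered retrospectively by one contact.

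The efficacy analysis sets aside PANSS scores taken more than 24 hours after stopping once the subject has switched to another antipsychotic. The adverse-event section has no matching rule, and no table separates events that began on treatment from events that began afterwards. An event on a later antipsychotic is therefore tabulated under the randomised arm. Under Section 14 a drug started more than one day after the last dose is a post-treatment medication. The shells have summary tables for prior and concomitant medications only, so that drug appears in Listing 16.2.1.9 and in no summary.

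At stake is the descriptive safety profile. Section 16 plans no treatment comparisons for safety unless a section says otherwise, so these percentages are the result that readers will use.

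**Working it through.** The SAP gives no figure for this point, so there is nothing to reproduce. The check sets the definitions side by side and then does arithmetic on the SAP's own durations.

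**1. Can the statements all hold?**
- Section 3.1 and Section 13: double-blind treatment is Day 1 to Day 42, and follow-up is a separate period after it.
- Section 16.1: the double-blind window for events ends when follow-up ends.
- Section 16.1.6: patch-site events are those in the double-blind period. Table 14.3.1.14 footnote: through follow-up.

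An event starting on Day 60 in a completer is a double-blind event in Table 14.3.1.2 but belongs to follow-up by onset date in Listing 16.2.3.1.1. For a patch-site event, a programmer cannot satisfy both Section 16.1.6 and the table footnote.

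**2. Share of counted time that is follow-up.** With D days on double-blind treatment, share = 30 / (D + 30).
- Completer, D = 42: 30 / 72 = 41.7%
- Stops at Day 7: 30 / 37 = 81%
- Stops at Day 14: 30 / 44 = 68%
- Stops at Day 21: 30 / 51 = 59%

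The early stopping days are examples, not SAP figures.

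**3. How much of the follow-up carries study drug?** Inputs: half-life 29.7 to 31.3 hours (Section 15.1.3). Five half-lives as negligible drug is an assumption, not an SAP rule.
- 5 × 29.7 / 24 = 6.2 days; 5 × 31.3 / 24 = 6.5 days
- Remaining follow-up: 30 − 6.2 = 23.8 days; 30 − 6.5 = 23.5 days
- As a share of a completer's 72 days: about 33% in both cases

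**4. Effect on the reported percentages.** If p is the on-treatment incidence and q the chance of the same event first arising in follow-up, taken as equal in all arms, the tabulated incidence is 1 − (1 − p)(1 − q). The difference between arms is then (p_active − p_placebo)(1 − q). With p assumed at 15% and 5%, the true difference is 10.0 points:

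| q (assumed) | Active | Placebo | Difference |
|---|---|---|---|
| 3% | 17.6% | 7.9% | 9.7 points |
| 5% | 19.3% | 9.8% | 9.5 points |
| 10% | 23.5% | 14.5% | 9.0 points |

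The level in each column rises, while the difference moves by 0.3 to 1.0 point. Every p and q here is an assumption; the SAP supplies none.

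**The case against.** A 30-day window after the last dose is common. This one is defined openly in Section 16.1 and restated in the footnotes, and Section 8 plans summaries that cover follow-up. Safety is reported as counts and percentages, a treatment-emergent count is temporal rather than causal, and investigator relatedness is tabulated separately. The discontinuation tables require that study drug was withdrawn (Section 16.1.2), so an event starting after the last patch should not enter them. Scale scores for extrapyramidal symptoms and akathisia, and weight, are summarised by visit and do not depend on this window. All of that stands. It does not remove the conflict between titles, period definitions and Section 16.1.6, and it does not supply an on-treatment incidence.

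Four stronger readings are tempting, and the documents do not support them:

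- **Drug-to-placebo ratios are materially diluted.** With the assumed rates above, the ratio falls from 3.0 to between 2.24 and 1.62. But the SAP reports no risk ratios, the rates are invented, and the risk difference barely moves. A single retrospective contact may also capture fewer events than such values of q imply.
- **Placebo events pushed over 5% distort the common-event table.** Section 16.1.5 includes a term that reaches 5% in any arm. An inflated placebo figure can only add a row.
- **Unequal dropout biases the comparison through the off-drug share.** Follow-up is 30 days for everyone and no output uses person-time, so the shares in step 2 are not the denominator of any table.
- **The window must be cut about 7 days after removal.** That length is a choice. It would also make observation time less equal: a Day 7 stopper against a completer is 37 against 72 days now (ratio 1.9), and 14 against 49 with such a cut (3.5). Applied to every table, it would shorten the serious and fatal tables (14.3.1.6 to 14.3.1.9) as well.

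**Conclusion.** The point holds as a defect of definition, labelling and tabulation. Collecting and counting adverse events through 30 days is not the error. The error is presenting them as double-blind-period events with no table that isolates on-treatment or follow-up onset, and with Section 16.1.6 contradicting the footnote of Table 14.3.1.14.

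The certain part comes from the SAP's own durations: 30 of 72 counted days for a completer are off study drug. That about 23.5 of those days carry negligible drug rests on the five-half-life convention. The effect on the reported percentages is unknown, because the SAP gives no switching rate and no event rates after a switch. The illustration suggests that risk differences would change little, while absolute percentages in every arm could rise. The efficacy analyses are not affected. The change is worth making because it is cheap and supplies a figure the plan lacks.

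**What to change.** 1. **Overview, serious and fatal tables** (14.3.1.1 and 14.3.1.6 to 14.3.1.9): keep the 30-day window and say in the titles that they run through the 30-day follow-up.
2. **SOC/PT tables, common-event tables and patch-site table** (14.3.1.2, 14.3.1.3 and 14.3.1.10 to 14.3.1.14): split by onset period with the existing double-blind/follow-up flag. Define the double-blind part as first double-blind patch through last patch removal. If the sponsor wants a washout tail, prespecify its length. Everything later goes under follow-up.
3. **Wording:** in Section 16.1, separate the overall 30-day treatment-emergent window from the double-blind onset period. Bring the footnotes of Table 14.3.1.1 and the adverse-event listings into line, and make Section 16.1.6 agree with the footnote of Table 14.3.1.14. In the same edit, reconcile the start of the window: the table footnotes admit events before the first double-blind dose, while Section 16.1 and the listing footnotes do not.

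**Cost:** SAP and shell wording, one date condition, and a few more rows or one extra table. No new data are needed and no event is dropped. The small downside is longer tables.

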### 16.1.1. ALL AES

Incidence of TEAEs will be presented by SOC and PT and also broken down further by maximum severity and relationship to study medication. Summaries will be sorted by incidence: by SOC and by PT within SOC.

#### 16.1.1.1. TEAEs by Relationship to Study Medication and Severity

Relationship, as indicated by the Investigator, is classed as "Unrelated", "Unlikely", "Possible", and "Probable" (increasing severity of relationship). A "Related" TEAE is defined as a TEAE with a relationship to study medication as "Possible" or "Probable". TEAEs with a missing relationship to study medication will be regarded "Related". If a subject reports the same AE more than once within a SOC/PT, the AE with the worst case relationship to study medication will be used in the corresponding summary.

Severity will be presented within Relationship. Severity is classed as mild/ moderate/ severe (increasing severity). TEAEs starting after the first dose of study medication with a missing severity will be classified as severe. If a subject reports a TEAE more than once within a SOC/PT at the worst relationship level, the AE with the worst severity will be used in the corresponding summary.

